relapses occur within the first few weeks of abstinence[19], this can be improved by recruiting quitters who have just quit, and starting the WhatsApp groups as soon as possible. Second, the intervention content and dosage through social media needs to be revised to increase participation. For instance, only 6 out of the 16 participants, who reported relapse at 2-month, shared their relapse experience in the group. The few number of reports of relapse posed barriers for early intervention. Due to limited number of eligible participants, some groups had only 2 to 5 participants, which led to inactive discussion. About one-fourth of the participants only stayed in the group, but did not post anything. These findings highlighted the importance of skilful and theory-driven group moderation, and inclusion of more updated and interesting content to increase the level of participation. Lastly, for a larger RCT, we shall add more recruitment sites to increase participant recruitment and generalizability. A subsequent cost-effectiveness analysis based on trial data will establish the optimal balance between costs and health effectiveness outcomes, and provide health economic data to policymakers to facilitate informed decision-making of health interventions for tobacco control

c) Aims and Hypotheses to be Tested:

This study aims to examine the effectiveness and cost-effectiveness of WhatsApp group discussion for smoking relapse prevention. To assess the effect due to treatment modality through the WhatsApp social group, we will analyse the frequency and topics of the posts in each social group and in each participant. The primary hypothesis is whether quitters who participate in the WhatsApp group discussion will have a higher prevalence of validated tobacco abstinence at 12-month follow-up than those who do not. Our second hypothesis is that greater participation in the social groups, indicated by number of posts received, posted and/or viewed, was associated with higher likelihood to quit at 12-month. The third hypothesis is that the WhatsApp intervention for a recent quitter is a more cost-effective option for tobacco abstinence and prolonged survival when compared to the control group.

d) Plan of Investigation:

(i) Subjects

Inclusion criteria:

- Smoke at least 1 cigarette per day at the service intake
- Aged 18 years or above
- Have enrolled or re-enrolled in the smoking cessation treatment for no more than 8 weeks
- No smoking for 7 to 14 days

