Simple individual randomization by sequentially numbered, opaque sealed envelopes (SNOSE) will be used to ensure the recruitment staff and the participants will be concealed to the allocation sequence before the group allocation. The principal investigator will prepare about 1,100 identical, opaque, sealed, A5-sized envelopes, with a unique 3-digit serial number on the cover of each envelope as an identifier. Half of them will contain a card indicating the intervention group, and the others will contain a card indicating the control group. When a participant is recruited, the research staff will open 1 envelope according the serial number to allocate the recruited participant, according to the card inside.

Interventions

When the research staff collects 10 participants in the intervention group (a few groups will have 11 participants), probably within one week, he/she will set up the WhatsApp group with them. Each WhatsApp group (about 50 groups in total) will allow real-time group discussion for 8 weeks. They will receive each week at least 3 text messages or videos from a moderator, which will be based on the six approaches delineated in “Treatments for the Recent Quitter” of the US Clinical Practice Guidelines on Treating Tobacco Use and Dependence[18]. Based on the Positive Psychology theories[20], and our experience of the FAMILY project, we developed a framework of four principles to enhance the online group moderation: (1) Using active listening skills to understand the thoughts and feelings behind participants’ sharing; (2) Showing sincere,

immediate, specific, and concrete appreciation and gratitude towards their sharing; (3) Mindful awareness of the group dynamics and giving strategic reactions; (4) Enhancement of self-efficacy, sense of control and satisfaction among the participants. In addition, if any participant shares their relapse experience in the group, the moderator will engage other participants to provide appreciation and support, or, if preferred, actively refer him/her to existing cessation services.

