To ensure quality assurance and intervention fidelity, all moderators will be provided a training of smoking cessation knowledge, and moderating skills to motivate participants to share. Our co-investigator ([name] [name]), who has the experience of using Positive Psychology theories in the FAMILY project, will train the moderators to use specific texts, “emoji” and short videos to express gratitude and appreciation towards participants’ sharing. Also, a research nurse will review the discussion contents, provide service referral for the participants who relapse, and organize case conference with the moderators each month to improve group moderation skills.

The control group will only receive 3 mobile phone text messages each week in the 8 weeks after recruitment. These message contents will be the same as those received by the intervention group. Our intervention will not interrupt the services that all participants will be receiving in the cessation clinics.

Follow-up

All participants will be followed up via telephone by an allocation-blinded interviewer at 3-, 6- and 12-month after the random group allocation. Only the participants who report abstinence in the past 7 days will be invited to provide samples of exhaled breath and/or saliva for biochemical validation at their residence, workplace or nearby, as preferred by the quitters. The Bedfont Smokerlyzer and iScreen OFD Cotinine Saliva Test Kit will be used for validations. To increase participation, the participants will be given HK\$100 (approximately equivalent to US\$12.8) as a compensation for their time cost. All participants will not know the validation incentive at baseline. The validation takes very short time (3 minutes) and is easy.

Allocation concealment

All recruitment staff and participants will be concealed to the group allocation at recruitment. The research staff will open the envelope of group allocation according to the serial number on the envelope, so he/she will not know the group sequence.

Blinding

Participants and group moderators cannot and will not be blinded to the intervention. Assessors of the follow-up outcomes and the research analysts will not be involved in the recruitment and intervention delivery, and will be blinded to the group allocation (single blindness).

Outcomes

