The primary outcome is biochemically validated (exhaled carbon monoxide < 4ppm; or/and saliva cotinine < 10ng/ml) tobacco abstinence at 12-month follow-up, which have been confirmed as a stringent criterion for abstinence verification for quitters who use nicotine replacement therapy^[21]. Secondary outcomes include prevalence of self-reported 7-day and continuous abstinence over the study period, and relapse rate, which is defined as the proportion of quitters who smoke at least 5 cigarettes in 3 consecutive days over the study period. Ancillary outcomes include change in frequency and intensity of smoking urge, change in the Minnesota Nicotine Withdrawal Scale (MNWS), and the change in HRQOL measured by Short-form 6-item instrument and EuroQoL 5-dimension 5-level (EQ-5D-5L) health utility scores from baseline to follow-ups. For cost-effectiveness analysis, the outcomes are the incremental cost-effectiveness ratio (ICER) in terms of cost per an additional tobacco abstinence gained for intervention compared to control group, and the ICER in terms of cost per life-years gain or quality-adjusted life-years gained for intervention versus control group.

(iii) Study design A pragmatic open-labelled 2-arm randomized controlled trial

(iv) Data processing and analysis

Statistical analysis

By intention-to-treat analysis (in line with CONSORT guideline), participants who are lost or refuse the follow-up will be treated as smokers with no changes in daily cigarette consumption. The analysis with multiple imputation (MI) procedure to impute the missing exhaled CO will be conducted as sensitivity analysis. Considering the correlated outcomes of participants within the same WhatsApp group, a post-hoc analysis by generalized estimating equation (GEE) model will be used to summarise the intervention effect with the odds ratios, with and without adjustment for baseline characteristics. Number needed to treat (NNT), which shows the number of treated subjects needed to have one additional quitter at 12-month, will be computed by taking the reciprocal of the risk difference between the 2 RCT groups. Number of posts received, posted or/and viewed in each participant and in each social group will be documented, and then included in the final GEE model to assess their association with the cessation outcome.

Text mining of the WhatsApp groups

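### Keep post counts out of the intervention-effect model, and test hypothesis 2 in a separate WhatsApp-arm model on early posts

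*Combined protocol and SAP*

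**What the plan says.** In the Combined protocol and SAP, section (iv), Statistical analysis, a single GEE model is introduced. It allows for correlation within WhatsApp groups and "will be used to summarise the intervention effect with the odds ratios, with and without adjustment for baseline characteristics". The NNT "will be computed by taking the reciprocal of the risk difference between the 2 RCT groups". The paragraph then turns to participation, where post counts are to be recorded at both the participant and the group level. Their use in the analysis is described in one clause: "and then included in the final GEE model to assess their association with the cessation outcome".

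The purpose of that last step is given in section c), where the statement of the second hypothesis reads: "greater participation in the social groups, indicated by number of posts received, posted and/or viewed, was associated with higher likelihood to quit at 12-month". No other test of this hypothesis is described.

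Under Interventions, posts come from a period after allocation and from one arm: "Each WhatsApp group (about 50 groups in total) will allow real-time group discussion for 8 weeks". For the other arm, "The control group will only receive 3 mobile phone text messages each week in the 8 weeks after recruitment".

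The plan does not say whether the post-count model covers one arm or both, how controls would be coded, whether the arm term stays in, or which weeks of posting count.

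**The concern.** Two problems follow from the wording.

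The first concerns the arm coefficient. The only GEE described before the post-count sentence is the intervention-effect model, and the post counts go into a model called final. Taken literally, a variable that arises after randomisation, and that is possible only in one arm, is added to the randomised comparison. The arm coefficient then no longer answers the primary question, and a reader could mistake it for the trial's adjusted result.

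The second concerns hypothesis 2 and does not depend on how the first is settled. Posts are counted over the same 8 weeks in which many relapses may occur. If people who relapse fall silent, low posting is partly a result of relapse and not a cause of it. More engaged people may also both post more and stay abstinent. Either mechanism gives a positive association when posting does nothing, and the plan describes no handling of either.

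**Working it through.** **1. The plan's own figures.** Inputs from Sample size calculation: 23.0% against 15.0%, two-sided 5%, 90% power, 1:1.

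- n per arm = [1.960·√(2·0.19·0.81) + 1.2816·√(0.23·0.77 + 0.15·0.85)]² / 0.08² = 503.3, so 504. This reproduces the plan, and the point does not change it.
- OR = (0.23/0.77)/(0.15/0.85) = 1.69.
- SE of log OR = √(1/115.9 + 1/388.1 + 1/75.6 + 1/428.4) = 0.164.

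**2. What the arm coefficient means with posts in the model.** Write logit P = a + b·arm + c·x, with x = log(1 + posts) and x = 0 for all controls. Controls inform only a. The WhatsApp arm alone determines a + b and c. So b is the log-odds of abstinence at zero posts in the WhatsApp arm minus the log-odds in controls. With an independence working correlation and no further covariates, c is the same whether controls are included or not. Restricting to the WhatsApp arm therefore removes the misleading b but cannot correct a misleading c.

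**3. Relapse that silences posting.** Assumptions, none from the documents: each member has a gamma-distributed posting rate, posts are Poisson over the weeks before relapse (at most 8), and posts have no effect on abstinence. True rates are 23% and 15%, with 504 per arm. The last column is arithmetic: odds = arm OR × 0.15/0.85, converted to a proportion.

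| Eventual smokers who relapse and go silent within 8 weeks | Arm OR without posts | Arm OR with posts | Posts p<0.05 | Implied abstinence at zero posts |
|---|---|---|---|---|
| 0% | about 1.70 | 1.69 | 7% | 23.0% |
| 30% | about 1.70 | 1.45 | 26% | 20.4% |
| 60% | about 1.70 | 1.18 | 83% | 17.2% |

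At 60%, fitting the WhatsApp arm alone leaves the 83% as it is, as step 2 predicts. Counting only posts from weeks 1-2 brings it down to 10%. Other assumed posting rates shift these percentages but not the pattern.

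**4. A different mechanism.** Here 300 trials per scenario were fitted by GEE with robust standard errors, with WhatsApp groups of about 10 and each control as a single cluster. Assumed: about 6 posts per member on average and about 21% posting nothing (the pilot, described in the Introduction, reports about one-fourth). An unmeasured engagement factor, correlated 0.7 with log posting intensity, acts on abstinence.

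| Scenario | Arm OR without / with posts | Power without / with posts | Posts OR per log unit | Posts p<0.05 |
|---|---|---|---|---|
| Posts unrelated to outcome | 1.69 / 1.72 | 89% / 73% | 0.98 | 9% |
| Engagement log-OR 0.5, posts inert | 1.72 / 1.15 | 91% / 11% | 1.33 | 81% |
| Engagement log-OR 1.0, posts inert | 1.68 / 0.76 | 91% / 20% | 1.71 | 100% |
| Whole effect runs through posts | 1.69 / 0.99 | 90% / 4% | 1.45 | 97% |

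In the 1.0 scenario, the 20% counts significant results in either direction. Even in the first row the SE of the arm coefficient rises from 0.163 to 0.211, a variance ratio of (0.211/0.163)² = 1.68. The last row, where the dose-response is real, looks like the two rows above it, so the model cannot tell them apart.

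**5. Group-level counts.** A count for the whole group is constant within it. With 504 members in groups of about 10, it has about 504/10 ≈ 50 independent values. Within a group, posts received plus own posts roughly equal the group total, so these variables are also nearly collinear if entered together.

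**The case against.** A reader might infer that the plan throws away its treatment effect. The documents do not support that. The effect odds ratios are planned without adjustment and with adjustment for baseline characteristics only, and post counts are not baseline characteristics. The NNT comes from the crude risk difference. The post counts serve a different stated purpose, the second hypothesis. Because that hypothesis speaks of participation in social groups, which controls do not have, a within-arm analysis is a natural reading. All of this stands, and on that reading the distorted arm coefficient never appears.

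A reader might also infer that any dose-response found will be spurious. That too goes beyond the documents. The association may be partly or wholly causal, and the plan words it as an association. The size of the bias rests on assumed posting behaviour. The pilot suggests that relapse does not always bring silence: 6 of the 16 participants who reported relapse at 2 months had shared it in the group. Someone who stops writing can still receive and read posts, so the figures for own posts do not carry over directly to those counts. Correlation within WhatsApp groups is already to be handled by the GEE.

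The objection does not remove the ambiguity about which model receives the post counts. Nor does it protect the test of hypothesis 2, which has the same weakness within the WhatsApp arm alone.

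**Conclusion.** The point holds in a limited form. The text allows post-randomisation counts into the intervention-effect model without restricting it to one arm. If both arms are kept with controls at zero, the resulting arm coefficient is not the intention-to-treat effect. The primary comparison survives provided the effect models are reported separately.

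The test of hypothesis 2 is exposed on either reading. With inert posts, the illustrations give a significant association in 7% to 83% of trials as early relapse with silence goes from 0% to 60%, and in 81% to 100% under unmeasured engagement. The arm OR in the joint model ranged from 1.72 down to 0.76. These are illustrations under assumed posting behaviour, not predictions; in the scenarios without relapse-silence or engagement confounding there was no material bias. This is a cheap improvement to a secondary analysis and does not invalidate the trial's main result.

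**What to change.** State that the intervention effect is estimated only from models that contain no post variable.

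Test hypothesis 2 in a separate model within the WhatsApp arm:
- use posts from an early window, for example weeks 1-2, which the archived discussions can supply;
- adjust for baseline predictors of abstinence;
- cluster by WhatsApp group, and treat group-level counts as having about 50 independent values;
- report the result as an observational association.

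If any model with both arms is kept, say how received messages are coded for controls, who get 3 × 8 = 24 texts.

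The cost is a few sentences of analysis plan and no new data collection. The downside is that fewer posts are counted, so the association is less precise. Some reverse causation from very early relapse remains. An early window also does not remove confounding by engagement, which is why the baseline adjustment and the observational label matter. Excluding members already relapsed at the end of the window is optional. Follow-up is at 3, 6 and 12 months, so that step is possible only if relapse dates are recorded.

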Cost-effectiveness analysis will be undertaken to indicate whether the intervention will be more cost-effective or even cost-saving option for a quitter over a time horizon of one year (within trial period) and lifetime. Within and lifetime cost-effectiveness analyses will be populated based on the healthcare provider perspective.

Model parameters input will be identified through within trial data and a review of local and overseas literature, where necessary. Within trial cost-effectiveness of WhatsApp intervention versus control group will be evaluated using total costs, the number of tobacco abstinence and total QALYs over the study period. EQ-5D-5L utility data at baseline and follow-ups from trial will estimate QALYs in two groups using area under the curve technique. Lifetime cost-effectiveness will be performed via Markov modelling that will simulate the annual health status progression of subjects in either intervention or control group (Appendix 8). Both the successful and unsuccessful quitters after the trial will be subject to the annual transition probability from a status of no diseases to lung cancer, cardiovascular diseases, and other diseases, and then mortality. Former smokers may be relapsed after abstinence. Discounting will only be applied to total costs and QALY calculation under the lifetime horizon. Sensitivity analyses will be conducted where each parameter will be set at plausible lower and upper bounds based on 95% confidence interval of estimates in above data analysis.

The incremental cost-effectiveness ratio (ICER) in terms of cost per an additional tobacco abstinence gained, life-years gained, or QALYs gained for the intervention group in comparison to the control group will be reported. The WhatsApp intervention will be considered as cost-

effective if its ICER will be less than 3 times per capita gross domestic product in Hong Kong recommended by WHO or the potential ICER threshold in Hong Kong. The cost-effectiveness model will be built using Microsoft Excel or Treeage Pro software.

[Word Count: 4,000]

e) Existing Facilities:

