 - 800 hours x 112 per hour incl. MPF /5 staff /9 months =\$1991 per staff per month
 - Total amount = \$1991 per month incl. MPF x 5 staff x 9 months = \$89,595
3. A part-time Registered Nurse (pt3, Nurse) with rich experience in smoking cessation:

- design intervention guidelines and the self-help booklet, providing training workshop to the recruitment staff and moderators (40 hrs x 2 months =80hrs)
 - hold case conference with the moderators, recruitment staff and telephone interviewers each month (4 hrs x 19 months =76hrs)
 - 80 hrs + 76 hrs x \$167 per hour incl. MPF /21 months=\$ 1241 per staff per month
 - Total amount = \$1,241 per month incl. MPF x 21 months =\$26,061
4. 10 part-time Student Research Assistants/ Technical Assistants (pt 2, Student RA/TA):
- Recruitment for subjects in clinics (4 hrs x 5 times per week x 30 weeks = 600 hrs)
 - Telephone follow-ups at 6-month and 12-month: 1,008 participants x 15 minutes x 2 follow-ups = 504 hrs;
 - Exhaled carbon monoxide (CO) validation at 6-month and 12-month: 504 intervention group participants x 23% quit rate = 116 participants; 504 control group participants x 15% quit rate = 76 participants, total: 192 quitters x 2 validations x 2 hrs = 768 hrs;
 - Total hours = 600hrs +504 hrs + 768 hrs = 1,872 hours
 - 1,872 hours x \$69 per hour incl. MPF / 10 staff / 19 months = \$680 per staff per month
 - Total amount =\$680 per month incl. MPF x 10 staff x 19 months = \$129,200

General Expenses - \$ 271,420

1. Conference (i.e. Travel and subsistence) (\$10,000)
2. Publication costs (\$20,000)
3. Audit fee (\$5,000)
4. Incentives for participants
Incentives for quitters who complete the exhaled CO validation at the 6-month and 12-month follow-ups: 504 intervention group participants x 23% quit rate = 116 participants; 504 control group participants x 15% quit rate = 76 participants, total: 192 quitters, 192 quitters x 2 validations x \$100 cash incentive = \$38,400
5. Incentives for participants who complete the telephone follow-up (1,008 participants x 2 follow-ups x \$50 supermarket coupon = \$100,800)
6. Incentive for participants who complete the in-depth interview (20 participants x \$300 = \$6,000)
 - Total = \$38,400 + \$100,800 + \$6,000 = \$145,200
7. Production of self-help booklet (1,100 booklets x \$5 = \$5,500)
8. Mobile phones for WhatsApp social group (3 phones x \$1,000 = 3,000)
9. CO monitors and mouthpieces for the validations (3 monitors x \$6000 = \$18,000)

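### The plan does not specify adjustment for baseline EQ-5D-5L utility when within-trial QALYs are compared; adding it costs nothing and improves precision

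*Combined protocol and SAP*

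**What the plan says.** The within-trial economic evaluation is described in section d)(iv), Cost-effectiveness analysis. It runs "over a time horizon of one year (within trial period) and lifetime". The within-trial comparison "will be evaluated using total costs, the number of tobacco abstinence and total QALYs over the study period". On QALYs there is one sentence: "EQ-5D-5L utility data at baseline and follow-ups from trial will estimate QALYs in two groups using area under the curve technique". No regression model, covariate or adjusted analysis is named for them. The sensitivity analysis is a parameter sweep: "Sensitivity analyses will be conducted where each parameter will be set at plausible lower and upper bounds", with the bounds taken from 95% confidence intervals.

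Baseline adjustment is mentioned once, in section d)(iv), Statistical analysis, for a GEE model that "will be used to summarise the intervention effect with the odds ratios, with and without adjustment for baseline characteristics". That model serves the binary abstinence outcome.

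Section d)(ii), Outcomes, lists as an ancillary outcome the change in "EuroQoL 5-dimension 5-level (EQ-5D-5L) health utility scores from baseline to follow-ups". Baseline utility is therefore to be measured, and section d)(ii), Procedures, places the baseline questionnaire before allocation. Section d)(ii), Follow-up, puts the contacts at "3-, 6- and 12-month after the random group allocation". The budget in section f) costs fewer: "Telephone follow-ups at 6-month and 12-month: 1,008 participants x 15 minutes x 2 follow-ups = 504 hrs".

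**The concern.** An area-under-the-curve QALY starts from the baseline value, so a difference between arms in baseline utility is counted directly in the QALY difference. It is also counted indirectly, because people with higher utility at baseline tend to have higher utility later. Randomization is simple and unstratified, so only chance balances baseline utility.

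If the arms' mean QALYs are simply subtracted, whatever imbalance occurs appears as a QALY gain or loss of the intervention and passes into the cost-per-QALY ratio. Any gain in utility from the intervention is spread over a difference of only 8 percentage points in abstinence, so the expected QALY difference may be small beside this noise. The parameter sweep would not remove the problem, because its bounds would be centred on the unadjusted estimate. The primary outcome is not involved.

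**Working it through.** **Plan's own figure.** The documents give no expected QALY difference to reproduce. The arm size used below comes from section d)(i), Sample size calculation: 23.0% versus 15.0%, two-sided 5%, power 90%, 1:1. The pooled z-test gives n = [1.960 × √(2 × 0.19 × 0.81) + 1.2816 × √(0.23 × 0.77 + 0.15 × 0.85)]² / 0.08² = 503.3, hence 504 per arm and 1,008 in total, as stated.

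**Inputs from the documents.** 504 per arm; 8-point difference in abstinence; one-year horizon; visits at 0, 3, 6 and 12 months (Follow-up) or 0, 6 and 12 months (budget).

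**Assumptions not in the documents.** Utility SD 0.10 to 0.20; equal correlation ρ between visits of 0.3 to 0.7; utility gain per additional quitter 0.02 to 0.10; the 8-point difference present at every follow-up; complete utility data; no clustering.

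**Step 1: trapezoid weights (years).** Visits 0, 3, 6, 12: 0.125, 0.25, 0.375, 0.25. Visits 0, 6, 12: 0.25, 0.5, 0.25. The baseline weight w₀ is 0.125 or 0.25.

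**Step 2: size of a chance baseline gap.** SE = SD × √(2/504) = SD × 0.0630, which is 0.0063, 0.0094 and 0.0126 for SD 0.10, 0.15 and 0.20.

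**Step 3: share carried into the unadjusted QALY difference.** b = w₀ + ρ(1 − w₀). With w₀ = 0.125 and ρ = 0.5, b = 0.125 + 0.5 × 0.875 = 0.5625. A one-SE gap then carries 0.5625 × 0.0063 = 0.0035 to 0.5625 × 0.0126 = 0.0071 QALY. Only 0.125 × 0.0063 = 0.0008 to 0.125 × 0.0126 = 0.0016 of this is baseline's own weight; the rest comes through the assumed correlation.

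**Step 4: precision gained by adjustment.** In units of the baseline SE squared, the unadjusted variance is V = ρ + (1 − ρ)Σw², and the adjusted variance is V − b². For visits 0, 3, 6, 12, Σw² = 0.28125.

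| ρ | V | b² | V − b² | SE reduction |
|---|---|---|---|---|
| 0.3 | 0.4969 | 0.1502 | 0.3467 | 16% |
| 0.5 | 0.6406 | 0.3164 | 0.3242 | 29% |
| 0.7 | 0.7844 | 0.5439 | 0.2405 | 45% |

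At ρ = 0.5 the SE of the QALY difference falls from 0.0050 to 0.0036 (SD 0.10), from 0.0076 to 0.0054 (SD 0.15) and from 0.0101 to 0.0072 (SD 0.20). With visits at 0, 6 and 12 months only, the variance reduction is 40% to 74%, against 30% to 69% with the 3-month visit.

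**Step 5: comparison with a possible effect.** Expected QALY difference = 0.08 × gain per quitter × (1 − w₀). With w₀ = 0.125 this is 0.0014, 0.0035 and 0.0070 for gains of 0.02, 0.05 and 0.10. The chance that the carried imbalance, in either direction, exceeds the effect is:

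| Gain per quitter | SD 0.15, ρ 0.5 | All assumed SD and ρ |
|---|---|---|
| 0.02 | 79% | 57% to 88% |
| 0.05 | 51% | 15% to 71% |
| 0.10 | 19% | under 1% to 45% |

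**The case against.** The strongest reply is that the plan has not made a wrong choice. The quoted sentence says how QALYs are constructed, not how the arms are compared, and area-under-the-curve QALYs are exactly the outcome that an adjusted regression would use. This stands: a reader might infer that the sponsor has decided to compare raw areas, but the text is silent.

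A reader might also infer that chance imbalance will outweigh the QALY effect. The documents cannot support that, because they give no utility SD, no between-visit correlation and no utility gain from quitting. With SD 0.10 and a gain of 0.10, even the full one-SE baseline gap (0.0063) is below the effect (0.0070).

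Nor does the unadjusted difference have a systematic bias: randomization makes it correct on average. Adjustment would not cure the low signal either. At ρ = 0.5 the adjusted SE is 0.0036 to 0.0072, still above the effects for gains of 0.02 and 0.05. The trial was sized for abstinence, not QALYs.

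Finally, it would be too strong to say that cost per QALY decides the third hypothesis. Section c) words that hypothesis in terms of abstinence and longer survival, and cost per QALY is one of several ratios to be reported. Baseline utility does not enter the cost per additional abstinence, and nothing in the documents makes it an input to life-years gained.

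What survives is narrower. The step from areas to an incremental QALY is unspecified, and the usual unadjusted subtraction would discard information that the trial already plans to collect.

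**Conclusion.** The point holds as a free improvement. The plan specifies no baseline-utility adjustment for the within-trial QALY difference, and the adjustment planned for the odds-ratio model does not extend to it. Left unadjusted, the difference carries realised imbalance into the cost-per-QALY ratio and has a larger standard error than necessary.

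The firmest figure is the reduction in that standard error: about 16% to 45%, and 29% at correlation 0.5, with visits at 0, 3, 6 and 12 months. The percentage depends on the visit schedule and the assumed equal correlation, not on the SD. The carried imbalance of 0.0035 to 0.0071 QALY depends in addition on the assumed SD of 0.10 to 0.20; whether it matches or exceeds the effect depends also on the assumed gain per quitter. If utility is collected only at the two budgeted follow-ups, baseline's weight doubles to 0.25 and the case for adjustment is somewhat stronger.

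Adjustment does not make the QALY comparison well powered. The primary outcome and the sample size of 1,008 are unaffected.

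**What to change.** In section d)(iv), Cost-effectiveness analysis, add that the incremental QALY will be estimated by regressing each participant's area-under-the-curve QALY on arm and baseline EQ-5D-5L utility, with standard errors that allow for WhatsApp group. State that this difference enters the within-trial cost-per-QALY ratio and that the unadjusted difference is reported as a sensitivity analysis. Naming the main estimate in advance also prevents a choice between the two after results are known.

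At the same time, reconcile the follow-up schedule in section d)(ii) with the budget in section f), and state at which contacts the EQ-5D-5L is collected, since this sets the weights in the area.

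The adjustment needs one or two sentences and no new data: baseline utility is already to be measured before allocation.
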